The regional pharmacy team started to handle free-text secure message requests for refills from parents of patients with PCPs in pediatrics during a pilot period starting April 11, 2024. Secure messages are different from RARs because they contain free text. These were found to be difficult to flag and send to the regional pharmacy team because accurately identifying the relevant secure messages required manual handling. The rate of such messages that could be identified per day would not have reached the intended sample size for this study. Thus, this study was designed to focus only on RARs, which are much simpler to identify consistently. The regional desktop medicine leader sent an email to the pediatric department at every facility to ask that during the study period, they ignore RARs from facilities randomized to Pharmacist Care, but continue to handle RARs from facilities randomized to Physician Care.

The formal study period will include patients with secure messages sent to the regional pharmacy team from May 6, 2024 to June 21, 2024 (7 weeks). The unit of analysis will be the RAR, allowing some patients to appear up to two times in the study cohort.

4.2. Intervention.

All procedures will be conducted as part of standard of care. In the Pharmacist Care group, each RAR for an ADHD medication will be assigned to a pharmacist on the regional team. Pharmacists will review requests using a standard protocol. They will call parents via telephone to elicit additional information where needed, file ADHD medication prescriptions where appropriate, and send follow-up secure messages.

In the PCP Care group, each ADHD medication RAR will be sent to the PCP. Physicians will review requests using the standard regional protocol (as well as any existing medical center-level protocols). Following this protocol, physicians call patients via telephone to elicit additional information where needed, file ADHD medication refill prescriptions when appropriate, and send follow-up secure messages.

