4.4. Main outcomes and measures

4.4.1. Outcomes

The primary outcome will be measured only among patients who have not had a weight recorded in the EHR during the 6 months (180 days) prior to the ADHD medication refill request. We will determine whether the prescribing clinician attempted to ensure that the child had a weight checked or recorded, counting the outcome as present if (a) the patient was referred for an in-person visit for a weight check (including a well child visit or a nurse visit for a weight check), or (b) had a parent-reported weight recorded in the EHR. This outcome will be assessed via analysis of EHR data and chart review. Referral for a visit or weight check (part a above) will include any of the following:

- (a) the EHR record or chart review indicates that an appropriate in-person appointment was booked with pediatrics, family medicine, or psychiatry after the pharmacist or PCP handled the message;
- (b) a chart note indicates that the pharmacist or physician handling the RAR instructed the parent to schedule a follow-up appointment for a weight check;
- (c) a note in the EHR indicates that a medical assistant or other staff member had attempted to book a follow-up appointment for a weight check

Secondary outcomes will be the:

- a. Whether the child had a weight recorded within 30 days after the RAR, regardless of the reason for the weight being measured (this measure would count weights recorded at urgent visits)
- b. Hours from the secure message request to the prescription order being placed, among patients who had a prescription ordered
- c. Days from the secure message request to the prescription being filled (sold), among patients who had a prescription ordered
- d. Parent satisfaction with care, as measured by standardized survey items

Exploratory outcomes will be:

- a. Whether the provider initially handling the request was able to fully resolve it without referring it to another provider (first-touch resolution)
- b. Whether the patient had a refill prescribed (% of patients with refills prescribed)

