We will also ask parents to indicate the mode by which they would prefer to make future ADHD medication refill requests, e.g. secure message or a telephone, video, or in-person appointment.

4.6. Statistical analysis plan.

The primary analysis will treat each patient as part of the group to which their facility was assigned (intention-to-treat). However, some patients in the Pharmacist Care group might have unintentional crossover and be handled by physicians instead of pharmacists. For this reason, we will conduct a secondary analysis in which patients are grouped based on the initial management approach they actually received (pharmacist or physician, based on which type of clinician first contacted the patient), similar to a per-protocol analysis. An RAR first accessed by a pharmacist and later accessed by physician will be counted in the pharmacist group.

The primary outcome is binary, i.e., whether or not a patient who had not had a weight check in the 6 months before the refill request is referred for an appropriate follow-up visit. This will be compared between study groups using mixed effects logistic regression providing point and interval estimates of outcome odds ratios associated with study group. This analysis technique accounts for the within-facility and within-patient correlation to obtain valid estimates of treatment effects and associated standard errors. The pre-specified set of covariates for inclusion in regression models include: study group and covariates used in the randomization procedure (i.e. patient socioeconomic status (using the Neighborhood Deprivation Index), patient age, sex, race and ethnicity, and comorbidity score). Study group and other covariates will be treated as fixed effects and facility will be handled as a random effect.

In addition, exploratory/sensitivity analyses will examine the impact of including additional covariates in our estimation of treatment effect, with focus on variables with chance imbalance in distributions by treatment group, as determined in preliminary analyses. Analyses resulting in

an appreciable change in the estimate of treatment differences or increased precision of the treatment effect will be noted.

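### A child referred at the first refill request but not yet weighed re-enters the primary analysis at the second, where the criteria read literally score a failure; this can attenuate the odds ratio (minor)

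*Combined protocol and SAP*

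**What the plan says.** Section 4.1 sets the unit: "The unit of analysis will be the RAR, allowing some patients to appear up to two times in the study cohort". The formal study period there is 7 weeks.

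Section 4.4.1 restricts the primary outcome to "patients who have not had a weight recorded in the EHR during the 6 months (180 days) prior to the ADHD medication refill request". The governing question is "whether the prescribing clinician attempted to ensure that the child had a weight checked or recorded". Success is either a referral for an in-person weight check or a parent-reported weight entered in the EHR. A referral is shown by any of three criteria:

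- (a) an appropriate "in-person appointment was booked with pediatrics, family medicine, or psychiatry after the pharmacist or PCP handled the message";
- (b) a chart note that "the pharmacist or physician handling the RAR instructed the parent to schedule a follow-up appointment for a weight check";
- (c) an EHR note that "a medical assistant or other staff member had attempted to book a follow-up appointment for a weight check".

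None of the three has an end date. Secondary outcome a does have one: "Whether the child had a weight recorded within 30 days after the RAR".

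Section 4.6 words the primary outcome per patient: "whether or not a patient who had not had a weight check in the 6 months before the refill request is referred". It says the mixed logistic model accounts for correlation within facility and within patient, but the only random effect it names is facility. Section 4.5 limits survey requests to the first RAR. No such limit, and no rule for repeats, is given for the primary outcome.

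**The concern.** Take a child who is referred at the first RAR, has not been weighed, and sends a second RAR inside the 7 weeks. The child still has no weight in the prior 180 days and so enters the denominator again. An appointment booked after the first RAR was booked before the second was handled, so criterion (a) read literally does not credit it. Criterion (b) looks to the clinician handling the present RAR. Criterion (c) might credit an old staff attempt, because it is tied to no RAR and no date. The governing sentence does not say whether an earlier attempt counts. Two chart reviewers following the plan could score this child differently.

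What is at stake is the primary odds ratio. If one arm refers more, it brings more already-referred, unweighed children to the second RAR. If they count as failures, that arm is penalised for having acted earlier.

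**Working it through.** **1. The plan's own figure.** Section 4.8 gives 95 patients (30% of 315), ICC 0.03, 1.5 patients per cluster, two-sided alpha 0.05 and 80% power, with a detectable rate of 77% against 50%. The design effect is 1 + 0.5 × 0.03 = 1.015, so each arm has 47.5/1.015 = 46.8 effective patients. The pooled-variance two-proportion formula then gives a detectable rate of 77.5%, and power of 78.4% at 77% vs 50%. The figure reproduces. The odds ratio is (0.77/0.23)/(0.50/0.50) = 3.35.

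**2. Assumed inputs.** None of these is in the documents. A share f = 10% or 30% of patients send a second RAR. Of children referred at the first RAR, 50% are weighed before the second; of those not referred, 10%. Children not referred the first time succeed at the second at their arm's rate p. A pending child (referred, unweighed) is re-referred or credited with chance r.

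**3. Formula, per arm.** Pending = 0.5p. Not referred and still unweighed = 0.9(1 − p).

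Pooled rate = [p + f(0.5p·r + 0.9(1 − p)p)] / [1 + f(0.5p + 0.9(1 − p))]

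**4. Worst case, r = 0.**

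- f = 10%, PCP Care: (0.50 + 0.1 × 0.225)/(1 + 0.1 × 0.70) = 0.5225/1.07 = 0.488.
- f = 10%, Pharmacist Care: (0.77 + 0.1 × 0.159)/(1 + 0.1 × 0.592) = 0.786/1.0592 = 0.742. Odds ratio 3.01.
- f = 30%: 0.5675/1.21 = 0.469 and 0.818/1.1776 = 0.694. Odds ratio 2.57.

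**5. Other scoring.** Power uses the pooled record counts, about 101 (f = 10%) and 113 (f = 30%). It treats repeats as independent apart from the ICC, which favours pooling.

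| Pending child at second RAR | OR, f = 10% | OR, f = 30% | Power, f = 10% / 30% |
|---|---|---|---|
| None credited or re-referred | 3.01 | 2.57 | 74.6% / 67.6% |
| Half | 3.17 | 2.90 | 77.5% / 76.0% |
| Three quarters | 3.26 | 3.11 | 78.9% / 80.0% |
| All | 3.35 | 3.37 | 80.3% / 83.8% |
| Re-referred at the arm's usual rate p | 3.35 | 3.35 | 80.8% / 84.9% |

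First RARs only, n = 95: power 78.4%.

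**6. Parent-reported weights.** These are successes, and they put a weight in the EHR, so such children do not re-qualify. If half of successes are of this kind (assumed), pending falls to 0.25p. The worst case becomes 3.17 or 2.89, and half credited becomes 3.26 or 3.10.

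**7. Sensitivity to the weighing rate, r = 0, no parent-reported weights.** If 25% of referred children are weighed: 2.88 or 2.35. If 75%: 3.17 or 2.89.

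**8. Against sampling error.** At n = 95 the standard error of the log odds ratio is about 0.45. The worst-case shift in step 4 is 0.23 or 0.58 standard errors; half credited is 0.12 or 0.32.

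**9. The plan's other scenario, 98% vs 80%.** The odds ratio is 12.25. With f = 10% and r = 0 the rates are 0.934 and 0.770, giving 4.25. Odds ratios move sharply near 100%; the difference itself goes only from 18 to about 16.5 points.

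**10. No true effect.** With 60% in both arms and equal handling the odds ratio is 1.00. If parent-reported weights are 60% of successes in one arm and 40% in the other, it lies between 0.97 and 1.04.

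**11. Within-patient correlation.** Simulating the facility-only model with 95 patients and strong patient effects (400 runs per setting) gave type I error of 5.0% to 6.0%. The Monte Carlo error is √(0.05 × 0.95/400) = 1.1 points.

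**The case against.** The best reply is that the scoring is fixed: the RAR is the unit, and criteria (a) and (b) look to what was done at that RAR. On this view a per-request odds ratio is a legitimate target that the plan chose, and its distance from the first-RAR odds ratio is not automatically bias. Each RAR is also reviewed under a protocol, so a fresh reminder at the second is plausible, and at the usual re-referral rate nothing is lost.

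Part of this stands. It removes the bias in that case and makes the worst case extreme, since it needs no pending child ever to get a documented reminder. It does not settle how an appointment already booked is scored, it leaves criterion (c) without a date, and it sits badly with a governing question about whether the clinician tried to get the child weighed.

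Three stronger readings are tempting, and the documents support none of them:

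- That the rule could create a false positive. With no true effect and equal handling the odds ratio stays at 1.00. A spurious effect needs arms that differ in referral route or re-referral practice, and even then it is small (step 10).
- That pooling repeats helps power only if nearly all pending children are credited. Under the assumptions of step 5, break-even with first RARs only is at about 65% credited.
- That the missing patient term invalidates the standard errors. The simulated type I error is hardly distinguishable from 5%.

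The survey's first-RAR rule governs survey requests only. It shows that such a rule is workable here, not that the primary outcome must follow it.

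**Conclusion.** The concern holds as a minor one. The plan lets a referred but unweighed child return to the denominator, and two of its three referral criteria, read literally, score that child as a failure unless a new action is documented. If the arms differ, this pulls the odds ratio toward 1: at 77% vs 50%, from 3.35 to 3.01 or 2.57 at worst, and to 3.17 or 2.89 if half of successes are parent-reported weights. Crediting the earlier referral leaves it essentially unchanged.

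These figures rest on assumed repeat, weighing and re-referral rates, and they are marginal odds ratios, not mixed-model estimates. Confidence in the gap in the text is high; confidence in its size is low. The mismatch in 4.6 between the within-patient statement and the facility-only random effect is real but of little numerical weight.

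The 95 used here rests on a 9-week period. The 7 weeks of section 4.1 give 35 × 7 × 0.30 = 73.5, about 74, where power for 77% vs 50% is about 68%. The 35 per week was itself a pilot estimate for secure messages, so the number of RARs may differ either way.

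**What to change.** - In 4.4.1, state that a referral or booking made in response to an earlier study RAR and still open at the second is credited, or that such RARs are not re-scored. Under the model above, leaving them out gives [p + f·0.9(1 − p)p]/[1 + f·0.9(1 − p)] = p, so the odds ratio stays at 3.35.
- Give criteria (a) and (c) a time window, and say in 4.4.1 and 4.6 whether the outcome is per RAR or per patient.
- Prespecify an analysis of each patient's first RAR in the study period as a sensitivity analysis. It could be primary if the sponsor accepts losing the repeat records: about 6 or 18 under the assumptions here, if the 315 counts patients.
- In 4.6, add a patient-level term or facility-robust standard errors, so that the model does what the text says.
- In 4.8, note that the 95 assumes 9 weeks and that 7 weeks gives about 74.

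The cost is SAP wording plus slightly more chart review and analysis. Nothing in the conduct of the trial changes.

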4.4. Main outcomes and measures

4.4.1. Outcomes

The primary outcome will be measured only among patients who have not had a weight recorded in the EHR during the 6 months (180 days) prior to the ADHD medication refill request. We will determine whether the prescribing clinician attempted to ensure that the child had a weight checked or recorded, counting the outcome as present if (a) the patient was referred for an in-person visit for a weight check (including a well child visit or a nurse visit for a weight check), or (b) had a parent-reported weight recorded in the EHR. This outcome will be assessed via analysis of EHR data and chart review. Referral for a visit or weight check (part a above) will include any of the following:

- (a) the EHR record or chart review indicates that an appropriate in-person appointment was booked with pediatrics, family medicine, or psychiatry after the pharmacist or PCP handled the message;
- (b) a chart note indicates that the pharmacist or physician handling the RAR instructed the parent to schedule a follow-up appointment for a weight check;
- (c) a note in the EHR indicates that a medical assistant or other staff member had attempted to book a follow-up appointment for a weight check

Secondary outcomes will be the:

- a. Whether the child had a weight recorded within 30 days after the RAR, regardless of the reason for the weight being measured (this measure would count weights recorded at urgent visits)
- b. Hours from the secure message request to the prescription order being placed, among patients who had a prescription ordered
- c. Days from the secure message request to the prescription being filled (sold), among patients who had a prescription ordered
- d. Parent satisfaction with care, as measured by standardized survey items

Exploratory outcomes will be:

- a. Whether the provider initially handling the request was able to fully resolve it without referring it to another provider (first-touch resolution)
- b. Whether the patient had a refill prescribed (% of patients with refills prescribed)

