Potential Results. We will test the hypotheses that Pharmacist Care compared with PCP Care will have higher quality of care, faster time to prescriptions and fills, and higher parent satisfaction.

Potential Conclusions and Relevance. If pharmacist care for ADHD medication refill requests has better or similar outcomes compared with PCP care, this will provide evidence supporting continuation of this approach. This study's findings will be useful for KPNC and to inform discussions about renewing the special extension of the Ryan Haight Act that allows this approach.

1. Specific Aims and Hypotheses

Enhancing message management and virtual urgent care options for patients are among TPMG and KFH's top priorities. As team-based inbox management is further developed, evaluating its clinical effectiveness and outcomes in terms of patient care experience and costs will provide valuable information for operational planning. In addition, sharing what we learn with other health care systems through talks and publications will help highlight TPMG's reputation as a group that innovates to support clinicians while increasing patient access through virtual care.

This study will compare the clinical outcomes and costs of two alternative modes of management of parent requests for refills of medications for attention deficit hyperactivity disorder (ADHD): management by a regional team of pharmacists, vs. management by primary care physicians. Patients will be included if they are younger than 18 years and if their parent's

secure message request was sent to a pediatrician or family medicine physician (but not to a psychiatrist). We will conduct a cluster randomized trial in 63 facilities in Kaiser Permanente Northern California to compare Pharmacist Care with Physician Care for patients with ADHD medication refill requests with regard to:

Aim 1. Quality of care

Example hypothesis: Patients without a weight recorded in the past 6 months will be more likely to receive referral for a follow-up weight check in the Pharmacist Care group than the Physician Care group.

Aim 2. Timeliness of care

Example hypothesis: Patients managed via Pharmacist Care will have a faster time to refill prescription than those managed via Physician Care.

Aim 3. Parent satisfaction

Example hypothesis: Parents in the Pharmacist Care group will report comparable satisfaction with the process compared with the Physician Care group.

2. Background and Significance

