For the secondary outcomes, we will compare the days from the secure message request to prescription order or medication fill between the Pharmacist Care and PCP Care groups using linear mixed regression models, providing point and interval estimates of between-group differences in mean outcomes. If the numbers of days have a skewed distribution, log transformation will be used. Analyses of other continuous secondary outcomes will be similar. The approach to inclusion of covariates and sensitivity/exploratory analyses is as described for Aim 1.

For patient satisfaction, care experience scores will be compared between the study groups using linear mixed effects regression with log transformation if needed for skewed data, with analyses paralleling that described for the secondary outcomes. For analyses, categorical responses will be combined into a binary variable (Excellent or Very Good vs. Good, Fair, or Poor).

For all aims, secondary analyses will assess variation in the estimates of treatment effect by age, sex, socioeconomic status (using the Neighborhood Deprivation Index), and race and ethnicity, via stratification by level of the potential effect modifier. These stratified analyses will inform the fitting of mixed effects regression models with appropriate cross-product terms between the potential effect modifier and study group indicator variable, allowing for a more formal assessment of heterogeneity in treatment effect.

A facility may drop out before completion of the study if they were assigned to PCP Care but add local pharmacist management, thus diverging from their assigned group. ADHD medication refill requests to such a facility will be censored as of the dropout date (the date that local pharmacist management began).

Tests of significance will be two-tailed with an alpha of .05. No Bonferroni or other formal correction for multiple comparisons will be used, but results will be interpreted with the multiple testing issue in mind.

4.8. Sample size and power. To estimate the available sample, we extrapolated from data analyzed during the pilot period in April 2024.

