Based on initial data in the pilot period, we estimate that the message pool handlers will send the regional pharmacy team 7 secure messages for straightforward ADHD medication refill requests per weekday, i.e., 35 eligible messages per week. We estimate based on expert opinion that 30% of these patients don't have a weight check in the previous 6 months. Assuming a 9-week evaluation period, the estimated sample size is 315 patients, or an average of 5 patients in each of the 63 clusters.

Given the group-randomization study design, calculation of sample sizes and minimum detectable treatment effects must account for the expected intraclass correlation (ICC) of observations within facilities. The ICCs in outcomes of interest are expected to be small, and therefore we present minimum detectable effects for an expected ICC of .03.

For Aim 1, the primary outcome is the % of patients without a weight check in the past 6 months who received referral for an appropriate follow-up visit. The following estimates assume that 30% of the 315 patients with secure messages will have not had a weight check in the past 6

months, for a sample size of 95 (63 clusters with 1.5 patients each). We also assume a desired power of 80%, a two-tailed alpha of 0.05 and an ICC of .03. If 50% of patients in the PCP Care group will receive an appropriate referral, the least detectable difference will 77%. If 80% of the patients in the PCP Care group receive an appropriate referral, the least detectable difference will be 98%. Thus, this sample size yields good power to identify only large differences between the two arms in the primary outcome.

For Aim 2, the outcome is days from the secure message to the prescription order. The following estimates assume a sample size of 315 (63 clusters with 5 patients each), a desired power of 80%, a two-tailed alpha of 0.05 and an ICC of .03. The least detectable effect size for a comparison of means will be 0.334. In other words, this study will have good power to find a statistically significant difference between the Pharmacist Care and PCP Care groups for a small to medium effect size.

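### Both timing outcomes are scored only among requests that ended in an order, a clinician decision made after randomisation, so the Aim 2 comparison is not fully protected by randomisation.

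*Combined protocol and SAP*

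**What the plan says.** Section 4.4.1 gives two timing outcomes with the same restriction: "Hours from the secure message request to the prescription order being placed, among patients who had a prescription ordered" and "Days from the secure message request to the prescription being filled (sold), among patients who had a prescription ordered". The same section lists as exploratory outcome (b) "Whether the patient had a refill prescribed (% of patients with refills prescribed", with no expected rate, direction or difference between arms.

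Section 4.2 leaves ordering to clinical judgement in both arms. Pharmacists on one regional team "file ADHD medication prescriptions where appropriate". In the comparison arm, "Physicians will review requests using the standard regional protocol (as well as any existing medical center-level protocols", and they too prescribe when they judge it appropriate.

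Section 1 (Aim 2) states a directional hypothesis: "Patients managed via Pharmacist Care will have a faster time to refill prescription than those managed via Physician Care". Section 4.6 analyses the times with "linear mixed regression models, providing point and interval estimates of between-group differences in mean outcomes", log-transformed if skewed. It assigns groups by intention to treat, and its sensitivity analyses add covariates. It gives no rule for a request with no order, no fixed horizon per request, and no sensitivity analysis for the restriction. Section 4.5 identifies orders and fills during the study period, again with no horizon per request. For Aim 2, Section 4.8 says "The following estimates assume a sample size of 315 (63 clusters with 5 patients each" and derives a least detectable effect of 0.334.

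**The concern.** Randomisation makes the two sets of requests comparable. It does not make the two sets of ordered requests comparable, because membership of those sets is decided after assignment by different kinds of clinician. Intention to treat puts each request in the right arm but does not bring back those excluded for want of an order.

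If requests that would have taken long are less likely to end in an order, and this happens more in one arm, that arm's mean time falls without anyone being served faster. If the never-ordered requests would have been quick ones, the shift goes the other way. With no horizon per request, a slow request that arrives late may also have no order within the study period and drop out, which would link exclusion to slowness.

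Timeliness is one of three aims, and the abstract says that better or similar outcomes will be taken as support for continuing pharmacist management. The power statement has a related mismatch: it counts every request, while the outcome counts only those with an order.

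**Working it through.** **Step 1. Reproduce the plan's figure.** Inputs from Section 4.8: 315 requests (157.5 per arm), 63 clusters of 5, ICC 0.03, 80% power, two-sided alpha 0.05.

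- Design effect: 1 + (5 − 1) × 0.03 = 1.12.
- Detectable difference: (1.9600 + 0.8416) × √(2 × 1.12 / 157.5) = 2.8016 × 0.1193 = 0.334 SD.

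This matches the plan. The values for means at ICC 0.01 and 0.05 in Appendix A (0.322 and 0.346) also reproduce. The arithmetic is sound for 315 analysed requests.

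**Step 2. Recompute for requests with an order.** Let a share p be ordered in both arms (assumed). Then N = 315p, the design effect is 1 + (5p − 1) × 0.03, and the detectable effect is 2.8016 × √(4 × design effect / N).

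| Share ordered | N | Design effect | Detectable effect (SD) |
|---|---|---|---|
| 100% | 315 | 1.12 | 0.334 |
| 95% | 299 | 1.1125 | 0.342 |
| 90% | 283.5 | 1.105 | 0.350 |
| 80% | 252 | 1.09 | 0.369 |
| 70% | 220.5 | 1.075 | 0.391 |

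**Step 3. Size of a false difference.** Give both arms the same standard normal (log) time, so the true difference is zero. A request is ordered if a score with correlation ρ to time falls below c, where Φ(c) = p. The mean time among ordered requests is then −ρ × φ(c)/p. The ratio φ(c)/p is 0.109, 0.195, 0.274, 0.350 and 0.497 for p = 0.95, 0.90, 0.85, 0.80 and 0.70.

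Example, 80% (Pharmacist) versus 90% (PCP) with ρ = 0.5: −0.5 × (0.350 − 0.195) = −0.077 SD.

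For the rejection rate, the variance of each arm's mean is [1 − ρ²(cλ + λ²)] × design effect / (157.5p), with λ = φ(c)/p. In the example the two terms are about 0.0077 and 0.0072, so the standard error is about 0.122. The two-sided test then rejects 9.7% of the time instead of 5%.

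| Ordered, Pharmacist vs PCP (assumed) | False difference, ρ = 0.3 to 0.7 (SD) | Rejection rate, no true difference |
|---|---|---|
| 90% vs 90%, same ρ | 0 | 5.0% |
| 85% vs 90% | −0.02 to −0.06 | 5.4% to 7.7% |
| 80% vs 90% | −0.05 to −0.11 | 6.6% to 15.4% |
| 70% vs 90% | −0.09 to −0.21 | 10.7% to 43% |
| 95% vs 85% | +0.05 to +0.12 | 6.9% to 17% |

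A negative value makes Pharmacist Care look faster; a negative ρ reverses every sign. With ρ = 0 in both arms the difference is zero at any rates. A simulation gave −0.077 for 80% versus 90% at ρ = 0.5 and −0.211 for 70% versus 90% at ρ = 0.7, in agreement with the formula.

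**Step 4. Equal rates are not enough.** If both arms order 90% but ρ is 0.7 in one and 0.3 in the other, the difference is (0.7 − 0.3) × 0.195 = 0.078 SD.

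**Step 5. Upper bounds.** If one arm loses exactly its slowest 5%, 10% or 20% (ρ = 1) and the other loses none, the shift is 0.109, 0.195 or 0.350 SD.

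**The case against.** A good deal can be said for the plan. Both arms work from a similar standard protocol, RARs are structured and carry no free text, and Section 4.8 describes the requests as straightforward. Large differences in who gets an order are therefore less likely, though the comparison arm may also apply local protocols. Exploratory outcome (b) would show a difference in ordering rates. It would not correct the timing estimate, and Step 4 shows that equal rates do not settle the matter.

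A reader might infer that requests passed from pharmacist to physician drop out of the comparison. The documents do not support that. The outcome runs to the order whoever places it, analysis is by assigned facility, and PCPs still receive Pharmacist-arm RARs in their inboxes (Section 4.2). A request passed on and later ordered keeps its full delay in its assigned arm. Only never-ordered requests are lost, and that these are the slow ones is an assumption.

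The power mismatch is modest beside the uncertainty in 315 itself. Section 4.1 gives a 7-week study period, while Section 4.8 assumes 9. At 35 requests per week, 7 weeks gives 245, for which the Step 2 formula gives about 0.373.

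Finally, counting never-ordered requests as not yet ordered changes the question, because proper declines then look like delay. That objection stands against replacing the ordered-only outcome. It does not stand against adding an all-request analysis.

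**Conclusion.** The point holds. The timing outcomes are conditioned on a post-randomisation decision, and the plan has no analysis that would show whether this matters. Bias needs two things together: selection that differs by arm, and a relation between ordering and time. Under the assumed rates and correlations it is small for a 5-point difference in ordering (at most 0.06 SD), moderate for 10 points (0.05–0.11 SD, or 14–32% of 0.334), and 0.09–0.21 SD for 20 points. The documents supply neither the rates nor the correlation, so the actual size is unknown.

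Three stronger readings are not supported. A reader might infer that the plan expects ordering to differ by arm; it only lists the proportion as an exploratory outcome. A reader might take 0.35 SD, which exceeds 0.334, as the likely bias; it is an upper bound, and none of the cases with ρ of 0.3 to 0.7 in the Step 3 table reaches 0.334. A reader might conclude that Aim 2 loses its randomised comparison altogether; its protection is weakened, and no bias arises if ordering is unrelated to time or both arms select alike.

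These are secondary outcomes, and the primary outcome is unaffected. The change should be made because Aim 2 carries a directional claim and the remedy is cheap.

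**What to change.** - Keep the ordered-only means for outcomes (b) and (c).
- Add a prespecified analysis of all RARs by assigned arm, up to a fixed time after each request that is chosen before outcome data are seen. Report the proportion ordered, and the proportion filled, by that time, together with the cumulative incidence or restricted mean time to the cut-off. Count never-ordered requests as not ordered at the cut-off, and account for facility clustering. An ordered but unfilled request, for which the plan states no rule, is treated likewise for fills.
- Show the proportion ordered and the share declined, by arm, beside the timing results.
- Draw the Aim 2 conclusion only if both analyses agree.
- Restate the Aim 2 detectable effect for the number of requests expected to have an order.

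If the data extract runs to the cut-off after the last request, the smaller of time-to-order and the cut-off is known for every RAR and can go into the linear mixed model already planned. The cost is SAP wording, with the same EHR sources; the share declined may need a rule for identifying it in the record. The downside is that properly declined requests count as not ordered, so the all-RAR result mixes prescribing rate with speed and must be read beside the declined share.
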